12.9.7 Observation of the statistical modelling assumptions

We will assume that the observed empirical data meets the statistical assumption for the theoretical distributional assumption required for the model that are fitted. The residuals from the statistical models will be plotted to observe any instances where the assumptions may have failed.

12.9.8 Per protocol population and analysis

We will carry out a complimentary secondary analysis of the primary outcome, using the per protocol population, this will exclude the set of patients that are coded as protocol violators. These will be due to: non-compliance; non-completion of instruments within the time-windows; non-compliance with the protocol in any other way.

12.9.9 Subgroup analyses

The primary outcome will be split by the following subgroup: Time-window; sex; baseline severity; different levels of compliance; concomitant recreational cannabis use.

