4.3 Trial Flowchart

Outcome	Screening	0	1	2	3	4
Week No.	-1 to -3	1	4	13	26	30
			(±3day)	(±7days)	(±14days)	(±7days)
Informed Consent	X					
Socio-demographic	X					
Information						
Medical History	X					
Physical examination	X	Х			Х	
(Vital Signs, ECG)						
Urine Drug Abuse		Х	Х			
Screen						

AUDIT, FTND, CEQ, SDS	X				X	
TFLB		X	X		X	
Cannabinoid levels in blood to confirm use of or abstinence from cannabis		X	X	X	X	
Pregnancy Test	Х	Х	Х	X	X	
Screening Blood Sampling- Clinical laboratory (Haematology & Biochemistry)	X				X	
Concomitant	Х	Х	X	X	X	
Medication						
Study Exclusion criteria check	X	X				
NART	Х					
Adverse Events		Х	X	X	X	X
Randomisation		Х				
Study Medication Dispensing		X	X	X		
Study Medication Compliance (pill count)			X	X	X	
Compliance Blood Sampling (Cannabidiol levels)		X	X	X	X	
Comprehensive Assessment of At-Risk Mental State	X	X	X	X	X	
Hospital Anxiety Depression Scale		X	X	X	X	
Global Functioning (Social and Role scales)		X			X	
UKU Side Effect Rating Scale		X	X	X	X	

5 Participants

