6.8 Subject Compliance

Compliance with CBD treatment will be assessed using pill-counts at visits 2, 3 and 4. Patients will be defined as complying in the presence of a pill count greater than 50% the expected number taken.

Furthermore, before the end of the study we will document a secondary measure of compliance by carrying out assay of CBD levels in blood at visits 1-4 in both arms of the study.

Patients who are defined as non-complying with the medication will be coded as protocol deviators.

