7.2 Baseline Visit (Randomisation, on Day 0): Following satisfactory completion of screening, patients will be randomised to one of the treatment arms in a double-blind manner. Before randomisation baseline measures (CAARMS and HADS including alcohol and drug use (in particular cannabis)⁶⁸⁻⁷⁰), physical examination and blood samples for cannabinoid levels and for Cannabidiol will be acquired. The participant will be randomised and study drugs dispensed from the local hub pharmacy. Side effects will also be assessed, by using the UKU side-effect rating scale ⁶³.

7.3 Month One Visit (Visit window 1, at approximately day 28): This visit will involve only clinical assessments, assessment of alcohol and drug use (in particular cannabis), blood sampling, monitoring of compliance, side effects, AEs, and dispensing of study drugs.

7.4 Month three Visit (Visit window 2, at approximately Day 91) and Month Six Visit (Visit window 3, at approximately Day 182): These visits will involve only clinical assessments, assessment of alcohol and drug use (in particular cannabis), blood sampling, monitoring of compliance and side effects as well as AEs. Study drugs will be dispensed as well on visit 3.

7.5 Month Seven Final safety visit (Visit window 4, at approximately Day 212): Only AEs will be recorded at this visit, via review of medical records.

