12.9.11 Patient completion compliance

Compliance will be determined as patient completion falling within the time windows provided in the Trial Flowchart.

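### Section 12.9.9 lists compliance level and concomitant cannabis use beside true baseline subgroups, so comparing arms within those strata is not a randomised comparison

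*Protocol*

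**What the plan says.** Section 12.9.9 of the protocol gives one undifferentiated list: "The primary outcome will be split by the following subgroup: Time-window; sex; baseline severity; different levels of compliance; concomitant recreational cannabis use". It does not mark any of these splits as exploratory or non-randomised.

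On compliance, section 6.8 says "Compliance with CBD treatment will be assessed using pill-counts at visits 2, 3 and 4" and "Patients will be defined as complying in the presence of a pill count greater than 50% the expected number taken". It adds a secondary measure, "carrying out assay of CBD levels in blood at visits 1-4 in both arms of the study". The Trial Flowchart (4.3) numbers the pill-count visits 1, 2 and 3 instead, but under either numbering every count follows the first dispensing at baseline.

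On cannabis, the flowchart has a row "Cannabinoid levels in blood to confirm use of or abstinence from cannabis", marked at visits 0, 1, 2 and 3. TFLB is marked at visits 0, 1 and 3, the urine drug screen at visits 0 and 1, and the CEQ and SDS at screening and visit 3. Sections 7.3 and 7.4 also place an assessment of cannabis use at months one, three and six. Section 12.9.9 does not say which of these values defines the subgroup.

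The term time-window is not defined in 12.9.9. Section 12.9.11 says "Compliance will be determined as patient completion falling within the time windows provided in the Trial Flowchart", and section 12.9.8 uses the term in the same sense. Sections 7.1 to 7.5 and 8.4.1, however, call the visits themselves visit windows -1 to 4.

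The primary analysis is by intention to treat (12.9.3), with a longitudinal mixed model adjusted for baseline severity and site (12.9.5.1).

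**The concern.** Randomisation makes the arms comparable within strata that are fixed beforehand. It gives no such guarantee within strata formed by what patients do after they start capsules. Sedation, lack of benefit or improvement may each change pill-taking, and they need not do so equally on CBD and placebo. Section 3.2.2 reports slightly more frequent mild sedation on CBD in the proof-of-concept studies, so an arm-specific reason for stopping is conceivable from the protocol's own text. If compliance levels were graded by blood CBD, the placebo arm would have no like-for-like group at all.

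The same holds for cannabis use recorded on treatment. If CBD changes use, a difference in effect between users and non-users may be a consequence of treatment rather than effect modification.

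What is at stake is interpretation. If the primary test is null, an apparent effect among patients who took their capsules is the result most likely to be quoted.

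**Working it through.** **1. Design figures (section 10.2).** Effect size 0.4, two-sided 0.05, 80% power:
n = 2 × (1.960 + 0.842)² / 0.4² = 98.1, so 99 per arm. The t-test version gives 99.08, so 100, as stated. With 32% dropout, 100 / 0.68 = 147.1, so 148 per arm and 296 in total, against 300 planned. The stated figures hold, and this point does not change them.

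**2. When each listed factor is known.**

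| Factor in 12.9.9 | Known before randomisation? |
|---|---|
| Sex | Yes |
| Baseline severity | Yes |
| Level of compliance | No (6.8) |
| Concomitant cannabis use | Measured before and after (4.3, 7.2 to 7.4); not tied to baseline |
| Time-window | Unclear: visit, or in-window completion |

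**3. Illustration with an inert drug.** Assumptions, none from the documents: outcome severity is standard normal; 30% are non-compliant in each arm; the log-odds of non-compliance rise by s per SD of severity, with s set separately by arm.

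Compliers with data: 150 × 0.68 × 0.70 = 71 per arm.

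Integrating severity over the compliers gives:
- s = 0: mean 0, variance 1
- s = 0.5: mean -0.143, variance 0.954
- s = 0.8: mean -0.213, variance 0.899

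The complier contrast (CBD minus placebo, negative favours CBD) is the difference of these means:

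| s on CBD | s on placebo | False complier effect, SD |
|---|---|---|
| 0.5 | 0 | -0.14 |
| 0.8 | 0 | -0.21 |
| 0.8 | 0.5 | -0.07 |
| 0.5 or 0.8 | same | 0.00 |
| 0.5 | 0.8 | +0.07 |
| 0 | 0.5 | +0.14 |
| 0 | 0.8 | +0.21 |

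Against the design effect: 0.14 / 0.4 = 35% and 0.21 / 0.4 = 53%.

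False-positive rate for selection on CBD only, unadjusted t-test:
- s = 0.5: 0.143 / √((0.954 + 1)/71) = 0.86 standard errors, so about 14%
- s = 0.8: 0.213 / √((0.899 + 1)/71) = 1.31 standard errors, so about 25%

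**4. Effect of baseline adjustment.** With selection on CBD only and s = 0.5 and 0.8:
- selection on outcome severity, assumed baseline-outcome correlation 0.5: -0.11 and -0.16
- the same with correlation 0.7: about -0.07 and -0.11
- selection acting only through baseline severity: 0.00

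**5. A second selection model.** 102 patients per arm (150 × 0.68), 70% compliers, 10,000 runs, no drug effect. Here r is the assumed correlation between the tendency to comply and a better outcome.

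| r placebo / CBD | Compliers, SD | Non-compliers, SD | Rejection in compliers |
|---|---|---|---|
| 0 / 0 and 0.3 / 0.3 | 0.00 | about 0 | 5% |
| 0 / 0.3 | -0.15 | +0.35 | 14% |
| 0 / 0.5 | -0.25 | +0.58 | 33% |
| -0.3 / 0.3 | -0.30 | +0.69 | 45% |

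The intention-to-treat comparison of all patients rejected in 5% to 6% of runs throughout.

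**The case against.** A reader might infer that three of the five subgroups are certainly post-randomisation. The documents do not support that. Only compliance is certain. Time-window may mean the visit, since the protocol names its visits that way and fits a longitudinal model. On that reading it asks for the effect by visit, which is legitimate and is not a patient subgroup. Cannabis use could be fixed at its baseline value in the statistical analysis plan. What stands is that the protocol wording points to use during treatment and does not restrict it.

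A reader might also take the word split to rule out an interaction test. It does not, and the choice of test is ordinary analysis-plan detail.

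Nor do the two uses of compliance, in 6.8 and 12.9.11, amount to a firm contradiction. The section titles differ, and 12.9.8 lists non-compliance separately from completion outside the windows.

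On size, a bias towards CBD needs selection that differs between the arms, and the case with selection on CBD only is the unfavourable side. Equal selection gives zero, reversed selection hides benefit, and baseline adjustment shrinks or removes the bias. Section 3.2.2 reports tolerability otherwise equal to placebo, which gives little support for strongly different selection. All of this stands, and it limits the size of the problem. It does not make the compliance split a randomised comparison.

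**Conclusion.** The point holds for compliance without qualification and for concomitant cannabis use on its natural reading. Following 12.9.9 as written can give a biased subgroup effect of CBD, in either direction. For an inert drug with 30% non-compliance and severity-related selection on CBD only, the false complier effect is about 0.14 to 0.21 SD unadjusted, and roughly 0.07 to 0.16 SD after baseline adjustment if selection acts on outcome severity. It is zero under equal selection. The slopes, the correlations and the 30% are assumptions, so these figures show what is possible, not what is expected.

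It would be wrong to infer that the trial's main conclusion is at risk: the intention-to-treat test and the sample size are untouched. This is a worthwhile correction to a supporting analysis. The per-protocol and sensitivity analyses (12.9.8, 12.9.10) exclude non-compliers, so they share the same selection and cannot serve as a check on it.

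**What to change.** - **Subgroups.** Limit 12.9.9 to sex, baseline CAARMS severity, and cannabis use fixed at its pre-randomisation value (CEQ and SDS at screening; TFLB, urine screen and blood cannabinoids at visit 0). Assess each by a treatment-by-subgroup interaction in the primary model.
- **Compliance.** Remove it as a subgroup. Report instead, as supportive, a complier-average causal effect with randomisation as instrument and pill-count compliance as exposure.
- **Time-window.** State the meaning. If it is the visit, report the effect by visit from the longitudinal model. If it is in-window completion, drop it as a subgroup.

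The cost is wording and one extra model, with no new data, and N stays at 300. There are three downsides.
- The causal estimate is less precise. Unadjusted, with 102 per arm and 70% compliers, its standard error is roughly √(2/102) / 0.70 = 0.20 SD, against √(2/71) = 0.17 SD for the naive complier split.
- Patients who take up to half their capsules count as non-compliers, which strains the assumption that allocation has no effect in them. A version using the amount taken, or another cut-off, should be shown alongside.
- Interaction tests are imprecise. For two equal subgroups (51 per arm each), the standard error is √(2 × 2/51) = 0.28 SD, so a non-significant interaction should not be read as showing equal effects.

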12.9.10 Sensitivity analysis

The primary outcome will be re-analysed to test our assumptions. Non-compliant will be considered protocol violators and excluded from analyses.

12.9.11 Patient completion compliance

Compliance will be determined as patient completion falling within the time windows provided in the Trial Flowchart.

12.9.12 Statistical Programming

All statistical programming will be using Stata (version 15, or later). All data manipulation will be carried out using the KCTU Statistics SOPs. In the generation of a statistical report., all syntax files will be held, alongside the data extract request, and data.

13 Quality Assurance

13.1 Monitoring

Monitoring of this trial will be to ensure compliance with Good Clinical Practice and scientific integrity will be managed and oversight retained, by the KHP-CTO Quality Team.

13.2 Notification of serious breaches of GCP and/or the protocol

In case of serious breaches of GCP and/or the protocol which compromise Safety or Physical; or mental integrity of the participants in the trial, or the scientific value of the trial, these will be reported in accordance with regulation 29A of the Medicine for Human Use (clinical Trials) Regulations (2004).

14 Trial Organisational Structure

14.1 Co-ordinating Team (CANTOP Clinical Trial Office)

The co-ordinating centre is based in The Department of Psychosis, Institute of Psychiatry, Psychology & Neuroscience, King's College London, and is chaired by the Chief investigator and co-ordinated by the Trial Manager (TM).

14.2 Trial Management Group (TMG)

The co-applicants, TM, and junior statistician consist of the TMG and meet monthly to determine how CANTOP is set up and conducted throughout the trial.

14.3 Trial Steering Committee

A Trial Steering Committee (TSC) will be appointed chaired by an experienced researcher in the area. Rest of the members will be selected according to guidelines from NIHR and will include a statistician and a patient or carer representative. Observers from the EME will be invited to attend all meetings and will be copied in on all committee papers. Meeting frequency will be agreed prior to study start but is likely to be at least annually, scheduled after DMC meetings. We will aim to minimise travel to meetings by using video conferencing.

14.5 Trial Data monitoring and Ethics Committee (DMC)

An independent **Data Monitoring Committee (DMC)** will be constituted to act in an advisory capacity to meet regularly to review accumulating data, monitor patient safety and make recommendations to the Trial Steering Committee. It will be chaired by an experienced clinician. The trial statistician will draft a Data Monitoring Committee Charter to ensure decisions on the way the committee functions are clearly documented and agreed prior to the start of patient recruitment. Meeting frequency will be agreed prior to study start but is likely to be at least annually. We will aim to minimise travel to meetings by using video conferencing.

15. Ethics

15.1 Ethics & Regulatory Approvals

The trial will be conducted in compliance with the principles of the Declaration of Helsinki (1996), the principles of GCP and in accordance with all applicable regulatory requirements including but not limited to the Research Governance Framework and the Medicines for Human Use (Clinical Trial) Regulations 2004, as amended in 2006 and any subsequent amendments.

This protocol and related documents will be submitted for review to XXXXXX Research Ethics Committee (REC), and to the Medicines and Healthcare products Regulatory Agency (MHRA) for Clinical Trial Authorisation.

The Chief Investigator will submit a final report at conclusion of the trial to the KHP-CTO (on behalf of the Sponsor), the REC and the MHRA within the timelines defined in the Regulations.

In case of protocol amendments, these will be communicated to the Sponsor, R&D office and sites' PIs.

15.2 Consent

Prior to screening, the Early Intervention Consultant will refer the patients who have expressed interest into the study to the study research team.

At screening, investigators will introduce the trial to patients. Patients will also receive Patient information sheets (PIS).

Qualified physicians will discuss the trial with patients in light of the information provided in the information sheets and give appropriate time for the participants to understand the information provided. Qualified physicians will obtain written informed consent from patients willing to participate in the trial.

15.2.1. Biological Samples

A materials consent will be obtained to specifically address the collection of routine blood samples and genotyping. After collection at the study site, routine blood samples will be delivered by the study research team to the local laboratory for analysis. Blood samples for study drug and cannabis use levels as well as genotyping will be stored locally and then shipped to the London hub for analysis.

16 Confidentiality

All study-related information will be stored securely at the study sites. All participant information will be stored in locked file cabinets in areas with limited access. All laboratory specimens, reports, data collection, process, and administrative forms will be identified by a coded ID [identification] number only to maintain participant confidentiality. All records that contain names or other personal identifiers, such as locator forms and informed consent forms, will be stored separately from study records identified by code number. All local databases will be secured with password-protected access systems. Forms, lists, logbooks, appointment books, and any other listings that link participant ID numbers to other identifying information will be stored in a separate, locked file in an area with limited access.

Participants' study information will not be released outside of the study without the written permission of the participant.

17 Access to data

17.1 Data handling

The Chief Investigator will act as custodian for the trial data. The following guidelines will be strictly adhered to:

Patient data will be pseudo-anonymised.

1. All pseudo-anonymised data will be stored on a password protected computer.

2. All trial data will be stored in line with the Medicines for Human Use (Clinical Trials) Amended Regulations 2006 and the Data Protection Act and archived in line with the Medicines for Human Use (Clinical Trials) Amended Regulations 2006 as defined in the Kings Health Partners Clinical Trials Office Archiving SOP

17.2. Direct Access to Source Data and Documents

Principal Investigators will have direct access to their own site's data sets and will have access to other sites data by request. To ensure confidentiality, data dispersed to study team members will be blinded of any identifying participant information consistent with the General Data Protection Regulation (GDPR).

The Investigator(s) will permit trial-related monitoring, audits, REC review, and regulatory inspections by providing the Sponsor(s), Regulators and REC direct access to source data and other documents (e.g. patients' case sheets, blood test reports, etc.).

18 Patient and Public Involvement (PPI)

Service users and carers have already identified early intervention as a research priority for the Maudsley Biomedical Research Centre for Mental Health at King's College London and South London & Maudsley NHS foundation trust

(https://www.ncbi.nlm.nih.gov/pubmed/27068151).

We also surveyed clinical high-risk of psychosis patients during our previous proof-ofconcept CBD study. Patients felt that their current treatments, often psychological and occasionally pharmacological (typically anxiolytic/antidepressant medications), were not optimal. One of the key priorities that they identified was the need for new pharmacological treatments that were safe and tolerated well, as opposed to currently available antipsychotic medications, which they found unacceptable owing to side effects. They also expressed an interest in taking CBD if it was found to be safe and effective and identified this as an important research priority.

Finally, for the current proposal a participant from our proof-of-concept study using CBD has been formally involved in the development of the application at the full application stage and has also agreed to be involved at the trial stage.

Patient and Public involvement will continue to be a critical part of the study. The aforementioned service user has agreed to be involved with practical aspects of developing the study protocol including training of research staff employed on the study, especially during CAARMS training and inter-rater reliability exercises and will also be part of our Patient Advisory Group. We are also in the process of establishing this group. We will also involve our service user group early on in supporting the issues of compliance.

Involving a service user group will ensure that the views of CHR patients and those with psychosis fully inform (i) every stage of the study especially at the planning stages (ii) practical aspects of the study protocol including patient information sheets such that these are feasible and easy to understand; and research visits and packaging of study drug are acceptable to the target population to maximize response, retention and compliance rates, and (iii) help interpret and disseminate study findings in a way that optimizes impact. Service users will be reimbursed for their time and expenses as per INVOLVE guideline.

19 Dissemination Policy

It is intended that the results of the study will be reported and disseminated at national/ international conferences and in peer-reviewed scientific journals. We aim to submit for publication the main results of the trial within two years of last patient recruitment.

Appendix "Protocol for the mechanistic sub-study"

1 Sub-study Synopsis

Title of clinical trial sub-study	CAN nabidiol as a T reatment f O r P sychosis clinical high-risk state- a R andomised C ontrolled Clinical T rial (CANTOP-RCT) mechanism Sub-Study
Protocol Short Title/Acronym	CANTOP-RCT SS
Purpose of clinical trial sub-study	To understand the neurochemical and neurophysiological basis of cannabidiol (CBD) effects added to treatment as usual, in people at clinical high- risk (CHR) of developing psychosis
Mechanism objective (s)	To test: When added to treatment as usual in CHR patients, whether the clinical effects of CBD are mediated by its effects on brain function and glutamate levels in the medial temporal cortex and basal ganglia
Endpoints	Secondary mechanism sub-study outcomes (measured at visit 1, day 28) : These outcomes will be based on measures made at visit 1, day 28, relative to those made at baseline: 1) Within-subject change in glutamate levels in the left hippocamus and caudate measured using ¹ H-MRS 2) Within-subject change in activation (indexed using the blood oxygen level dependent signal; BOLD) in the medial temporal cortex (MTL) and basal ganglia during a verbal memory task, and during an emotional (fear) processing task. 3) Within-subject change in resting state MTL and basal ganglia perfusion, as indexed using arterial spin labelling (ASL).
Sample Size	One hundred (Total N=100; n=50 each from the CBD and placebo treatment arms) CHR-APS patients drawn from the main clinical trial
Version and date of protocol Protocol Development (amendments, version date)	Version 1, 10 th January 2018 Not applicable

2 Background & Rationale

Previous research data and proof-of concept studies suggest that the therapeutic effects of CBD may reflect its ability to correct neurophysiological abnormalities in the medial temporal cortex and striatum. We therefore propose to investigate this further in a mechanism study, nested within a fully powered RCT. As well as advancing our understanding of the mechanism of action of CBD, assessing brain function prior to treatment might also help to predict which CHR patients will respond best to treatment with CBD. At present there is no way of predicting this on clinical grounds, but recent evidence from studies in psychosis suggests that neuroimaging measures can distinguish patients who will or will not respond to antipsychotic medication¹.

3 Trial Sub-Study Objectives

We aim to understand the neurochemical and neurophysiological mechanisms through which CBD exerts its beneficial effects in CHR patients.

